**DREAM study protocol - Comparison 11 Anastrozole vs Exemestane or Letrozole**

- Maximum allowed follow-up time (1095 days) reached

## 7. Propensity score analysis

We will use a propensity-score (PS)-based approach to account for measured confounding in this study. The PS will be calculated as the predicted probability of initiating the exposure of interest (i.e., the repurposing candidate) versus the reference drug conditional on baseline covariates using multivariable logistic regression constructed separately in each data source. On average, patients with similar PSs have similar distribution of potential confounders used to estimate the PS. Therefore, analyses conditioned on the PS provide effect estimates that are free from measured confounding. For all our analyses, initiators of each exposure of interest will be matched with initiators of the reference exposure based on their PS within each data source. Pair matching will be conducted using a nearest-neighbor algorithm, which seeks to minimize the distance between propensity scores in each pair of treated and reference patients, and a caliper of 0.025 on the natural scale of the PS will be used to ensure similarity between the matched patients.

We report multiple diagnostics for PS analysis in this protocol. First, the PS distributional overlap is provided between two groups before and after matching to ensure comparability of these groups. Next, balance in each individual covariate between two treatment groups is reported using standardized differences.

## 8. Table for covariate balance

	Crude			PS-Matched		
Variable	Anastrozole (N = 10,926)	Exemestane or Letrozole (N = 6,063)	St. Diff	Anastrozole (N = 5,508)	Exemestane or Letrozole (N = 5,508)	St. Diff
Demographics						
Age, mean (SD)	73.7 (6.1)	73.8 (6.3)	-0.02	73.9 (6.4)	73.9 (6.3)	0.01
Gender, n (%)						
Male	41 (0.4)	40 (0.7)	-0.04	29 (0.5)	28 (0.5)	0.00
Female	10885 (99.6)	6023 (99.3)	0.04	5479 (99.5)	5480 (99.5)	0.00
Race, n (%)						
White	9669 (88.5)	5351 (88.3)	0.01	4820 (87.5)	4855 (88.1)	-0.02
Black	744 (6.8)	407 (6.7)	0.00	400 (7.3)	379 (6.9)	0.02
Hispanic	96 (0.9)	56 (0.9)	-0.01	60 (1.1)	51 (0.9)	0.02
Other	417 (3.8)	249 (4.1)	-0.02	228 (4.1)	223 (4)	0.01
Region, n (%)						
Northeast; n (%)	2188 (20)	1168 (19.3)	0.02	1086 (19.7)	1080 (19.6)	0.00
South; n (%)	3912 (35.8)	2431 (40.1)	-0.09	2174 (39.5)	2156 (39.1)	0.01
Midwest; n (%)	2877 (26.3)	1266 (20.9)	0.13	1207 (21.9)	1210 (22)	0.00
West; n (%)	1936 (17.7)	1189 (19.6)	-0.05	1035 (18.8)	1053 (19.1)	-0.01
Other; n (%)	13 (0.1)	9 (0.1)	-0.01	6 (0.1)	9 (0.2)	-0.02
Calendar year of index date, n (%)						
2014	2409 (22)	1313 (21.7)	0.01	1160 (21.1)	1222 (22.2)	-0.03
2015	2470 (22.6)	1326 (21.9)	0.02	1217 (22.1)	1211 (22)	0.00
2016	2154 (19.7)	1210 (20)	-0.01	1135 (20.6)	1102 (20)	0.02

DREAM study protocol - Comparison 11 Anastrozole vs Exemestane or Letrozole

2017	1950 (17.8)	1110 (18.3)	-0.01	1001 (18.2)	992 (18)	0.00
2018	1943 (17.8)	1104 (18.2)	-0.01	995 (18.1)	981 (17.8)	0.01
Low income subsidy, n (%)	1197 (11)	645 (10.6)	0.01	632 (11.5)	582 (10.6)	0.03
Dementia risk factors, n (%)						
Anxiety	2220 (20.3)	1238 (20.4)	0.00	1142 (20.7)	1125 (20.4)	0.01
Bipolar disorder	109 (1)	71 (1.2)	-0.02	63 (1.1)	61 (1.1)	0.00
Coronary artery disease	1985 (18.2)	1111 (18.3)	0.00	1011 (18.4)	1008 (18.3)	0.00
Depression	1887 (17.3)	1083 (17.9)	-0.02	991 (18)	978 (17.8)	0.01
Diabetes	3114 (28.5)	1788 (29.5)	-0.02	1599 (29)	1621 (29.4)	-0.01
Hypertension	8496 (77.8)	4606 (76)	0.04	4236 (76.9)	4228 (76.8)	0.00
Obesity	2518 (23)	1306 (21.5)	0.04	1249 (22.7)	1223 (22.2)	0.01
Schizophrenia	19 (0.2)	9 (0.1)	0.01	12 (0.2)	9 (0.2)	0.01
Markers for healthy behavior, frailty, healthcare use						
Bone mineral density test, n (%)	4106 (37.6)	1926 (31.8)	0.12	1876 (34.1)	1855 (33.7)	0.01
Colonoscopy, n (%)	1030 (9.4)	601 (9.9)	-0.02	551 (10)	543 (9.9)	0.01
Fecal occult blood test, n (%)	1033 (9.5)	563 (9.3)	0.01	538 (9.8)	524 (9.5)	0.01
Herpes zoster vaccination, n (%)	6 (0.1)	2 (0)	0.01	2 (0)	2 (0)	0.00
Influenza vaccination, n (%)	7203 (65.9)	3926 (64.8)	0.03	3613 (65.6)	3589 (65.2)	0.01
Mammography, n (%)	6944 (63.6)	3291 (54.3)	0.19	3159 (57.4)	3163 (57.4)	0.00
Pneumococcal vaccination, n (%)	4881 (44.7)	2651 (43.7)	0.02	2464 (44.7)	2427 (44.1)	0.01
Smoking, n (%)	3320 (30.4)	1820 (30)	0.01	1713 (31.1)	1666 (30.2)	0.02
Number of C-reactive protein tests ordered, mean (SD)	0.1 (0.6)	0.1 (0.6)	-0.01	0.1 (0.6)	0.1 (0.6)	0.00

DREAM study protocol - Comparison 11 Anastrozole vs Exemestane or Letrozole

Number of emergency room visits, mean (SD)	0.5 (0.9)	0.5 (1)	-0.05	0.5 (0.9)	0.5 (1)	-0.02
Number of distinct prescriptions, mean (SD)	10.9 (5.5)	11 (5.7)	-0.01	10.9 (5.6)	11 (5.7)	-0.01
Number of hospitalizations, mean (SD)	0.2 (0.5)	0.2 (0.5)	-0.03	0.2 (0.5)	0.2 (0.5)	-0.01
Number of outpatient visits, mean (SD)	14.4 (8.2)	14.9 (8.7)	-0.06	14.5 (8.5)	14.7 (8.5)	-0.02
Number of physician office visits, mean (SD)	14.4 (8.2)	14.9 (8.7)	-0.06	14.5 (8.5)	14.7 (8.5)	-0.02
Number of serum creatinine tests ordered, mean (SD)	1.4 (2.1)	1.4 (2)	0.01	1.4 (2)	1.4 (1.9)	0.01
Composite frailty score, mean (SD)	0.2 (0)	0.2 (0)	-0.06	0.2 (0)	0.2 (0)	-0.01
Falls, n (%)	525 (4.8)	299 (4.9)	-0.01	265 (4.8)	272 (4.9)	-0.01
Fractures, n (%)	723 (6.6)	481 (7.9)	-0.05	384 (7)	395 (7.2)	-0.01
Osteoporosis, n (%)	2535 (23.2)	1371 (22.6)	0.01	1256 (22.8)	1261 (22.9)	0.00
Use of supplemental oxygen, n (%)	138 (1.3)	55 (0.9)	0.03	49 (0.9)	54 (1)	-0.01
Combined comorbidity score, mean (SD)	3.4 (3.1)	4.1 (3.3)	-0.24	3.8 (3.2)	3.8 (3.2)	0.01
Comedication use, n (%)						
Angiotensin converting enzyme inhibitors (ACEi)	2867 (26.2)	1519 (25.1)	0.03	1395 (25.3)	1398 (25.4)	0.00
Angiotensin II receptor blockers (ARBs)	2716 (24.9)	1474 (24.3)	0.01	1369 (24.9)	1360 (24.7)	0.00
Antidepressants	3036 (27.8)	1726 (28.5)	-0.02	1521 (27.6)	1550 (28.1)	-0.01
Beta blockers	3625 (33.2)	2040 (33.6)	-0.01	1867 (33.9)	1855 (33.7)	0.01

DREAM study protocol - Comparison 11 Anastrozole vs Exemestane or Letrozole

Calcium channel blockers	2513 (23)	1357 (22.4)	0.02	1250 (22.7)	1259 (22.9)	0.00
DMARD	334 (3.1)	170 (2.8)	0.02	157 (2.9)	160 (2.9)	0.00
Diuretics	4685 (42.9)	2467 (40.7)	0.04	2286 (41.5)	2292 (41.6)	0.00
Insulin	583 (5.3)	325 (5.4)	0.00	291 (5.3)	301 (5.5)	-0.01
Lipid lowering drugs	5814 (53.2)	3070 (50.6)	0.05	2843 (51.6)	2846 (51.7)	0.00
Nitrates	391 (3.6)	222 (3.7)	0.00	193 (3.5)	203 (3.7)	-0.01
Non-insulin diabetes medications	1847 (16.9)	1068 (17.6)	-0.02	957 (17.4)	965 (17.5)	0.00
SAMA/SABA	1336 (12.2)	744 (12.3)	0.00	680 (12.3)	670 (12.2)	0.01
Anticoagulants	986 (9)	549 (9.1)	0.00	494 (9)	511 (9.3)	-0.01
Anti-epileptic mood stabilizers	117 (1.1)	62 (1)	0.01	57 (1)	56 (1)	0.00
Antiplatelet agents	528 (4.8)	274 (4.5)	0.02	256 (4.6)	263 (4.8)	-0.01
Atypical antipsychotics	157 (1.4)	103 (1.7)	-0.02	91 (1.7)	92 (1.7)	0.00
Benzodiazepines	2888 (26.4)	1674 (27.6)	-0.03	1499 (27.2)	1520 (27.6)	-0.01
Lithium	13 (0.1)	12 (0.2)	-0.02	9 (0.2)	10 (0.2)	0.00
Anti-epileptics (other than mood stabilizers)	1431 (13.1)	807 (13.3)	-0.01	701 (12.7)	728 (13.2)	-0.02
Serotonin-norepinephrine reuptake inhibitors	655 (6)	399 (6.6)	-0.02	345 (6.3)	346 (6.3)	0.00
Selective serotonin reuptake inhibitors	1828 (16.7)	1083 (17.9)	-0.03	953 (17.3)	973 (17.7)	-0.01
Tricyclic antidepressants (TCAs)	345 (3.2)	172 (2.8)	0.02	141 (2.6)	157 (2.9)	-0.02
Typical antipsychotics	23 (0.2)	20 (0.3)	-0.02	15 (0.3)	18 (0.3)	-0.01
Breast Cancer Variables , n (%)						
Breast surgery	9099 (83.3)	3988 (65.8)	0.41	3980 (72.3)	3977 (72.2)	0.00
Chemotherapy	2120 (19.4)	1460 (24.1)	-0.11	1203 (21.8)	1205 (21.9)	0.00

DREAM study protocol - Comparison 11 Anastrozole vs Exemestane or Letrozole

Hormone therapy agents	1088 (10)	865 (14.3)	-0.13	682 (12.4)	682 (12.4)	0.00
Immunotherapy	1 (0)	1 (0)	-0.01	1 (0)	1 (0)	0.00
Radiation therapy	5121 (46.9)	2299 (37.9)	0.18	2228 (40.5)	2236 (40.6)	0.00
Targeted therapy	34 (0.3)	232 (3.8)	-0.25	34 (0.6)	34 (0.6)	0.00
Comorbid conditions, n (%)						
Atrial fibrillation	1081 (9.9)	589 (9.7)	0.01	556 (10.1)	553 (10)	0.00
Asthma	1820 (16.7)	988 (16.3)	0.01	906 (16.4)	891 (16.2)	0.01
Chronic obstructive pulmonary disease	1804 (16.5)	1019 (16.8)	-0.01	932 (16.9)	913 (16.6)	0.01
Chronic liver disease	917 (8.4)	650 (10.7)	-0.08	533 (9.7)	538 (9.8)	0.00
Drug or alcohol abuse or dependence	985 (9)	518 (8.5)	0.02	491 (8.9)	477 (8.7)	0.01
Heart failure	714 (6.5)	414 (6.8)	-0.01	361 (6.6)	375 (6.8)	-0.01
Hyperlipidemia	7634 (69.9)	4107 (67.7)	0.05	3738 (67.9)	3778 (68.6)	-0.02
Ischemic heart disease	1919 (17.6)	1073 (17.7)	0.00	975 (17.7)	974 (17.7)	0.00
Malignancy	10906 (99.8)	6054 (99.9)	-0.01	5500 (99.9)	5499 (99.8)	0.01
Peripheral vascular disease	754 (6.9)	422 (7)	0.00	392 (7.1)	394 (7.2)	0.00
Rheumatoid Arthritis	357 (3.3)	210 (3.5)	-0.01	186 (3.4)	196 (3.6)	-0.01
Renal dysfunction	1319 (12.1)	723 (11.9)	0.01	666 (12.1)	660 (12)	0.00
Stroke or transient ischemic attack	736 (6.7)	442 (7.3)	-0.02	399 (7.2)	397 (7.2)	0.00
Venous thromboembolism	478 (4.4)	279 (4.6)	-0.01	231 (4.2)	250 (4.5)	-0.02

## 9. Statistical analysis plans

Incidence rates for the outcome will be estimated for the treatment and reference groups before and after PS matching. The competing risk of death could be of concern for the current set of analyses if mortality is frequent among patients included in the cohort and if differences in the risk of mortality between treatment and reference groups are substantial. In the PS-matched sample, we will use cause-specific hazard models to provide hazard ratios averaged over the entire follow-up period as well as interval specific hazard ratios (1, 2, and 3 years) for the association between the treatment of interest and risk of ADRD after considering all-cause mortality as a competing event. Pre-specified subgroup analyses will be conducted based on age, sex, and baseline cardiovascular disease.

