## 3. Data Source(s)

Medicare, 2008-2018

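### The age and cardiovascular-disease subgroup hazard ratios appear to reuse one whole-cohort propensity-score match, so covariate balance inside each subgroup is neither guaranteed nor checked

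*Combined protocol and SAP*

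**What the plan says.** Section 9 gives the subgroups one sentence: "Pre-specified subgroup analyses will be conducted based on age, sex, and baseline cardiovascular disease". It states no age cut, no definition of cardiovascular disease and no way of forming the subgroup sets. Earlier in the same paragraph it fixes the sample for estimation: "In the PS-matched sample, we will use cause-specific hazard models".

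Section 7 sets the level at which that sample is built. The PS is estimated "conditional on baseline covariates using multivariable logistic regression constructed separately in each data source". The scope is wide: "For all our analyses, initiators of each exposure of interest will be matched". Pairs are "matched with initiators of the reference exposure based on their PS within each data source". The algorithm is also given: "Pair matching will be conducted using a nearest-neighbor algorithm", with a caliper of 0.025 on the PS scale. Section 3 lists a single source, "Medicare, 2008-2018", which implies one PS and one match per analysis cohort.

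Section 7 promises PS overlap plots and standardized differences between the two treatment groups. Section 8 shows these differences for all 5,508 matched pairs and for no subgroup.

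**The concern.** Pairs are formed on the PS alone, not on age group or cardiovascular disease. Once the matched sample is cut by either variable, balance within a stratum no longer comes from the matching design. It depends on the PS model describing treatment choice correctly in that stratum. Section 7 does not say whether the model contains interactions.

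Breast surgery is the covariate to watch, because it has the largest crude imbalance in Section 8 and is listed among the breast cancer treatment and severity variables. If its link to drug choice differs by age and the PS model does not capture this, an excess of surgery in one arm among older patients can be offset by a deficit among younger patients. The whole-cohort difference then reads 0.00. Each subgroup hazard ratio would carry some confounding, in opposite directions. That could look like effect modification where there is none, or mask it where it exists, and effect modification is what subgroup analyses are meant to show.

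**Working it through.** **1. Overall balance reproduces.** Inputs are the Section 8 counts. The standardized difference is d = (p1 − p0) / √{[p1(1 − p1) + p0(1 − p0)] / 2}.
- Breast surgery, crude: 9,099/10,926 = 0.833 and 3,988/6,063 = 0.658, so d = 0.41, as printed.
- Breast surgery, matched: 3,980/5,508 and 3,977/5,508, so d = 0.00, as printed.
- Crude odds ratio for surgery: (9,099/1,827) / (3,988/2,075) = 2.59, log 0.95.

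**2. How far pairs agree on the subgroup variables.** Crude differences are −0.02 for age and 0.00 for coronary artery disease, so the PS says little about either. If pair members are close to independent on the variable, the expected share of split pairs is p(1 − q) + q(1 − p), where p and q are the prevalences in the matched arms.
- Coronary artery disease (1,011 and 1,008 of 5,508): 0.1836 × 0.8170 + 0.1830 × 0.8164 = 0.299, about 1,650 pairs.
- Age 75 or over (cut assumed; normal approximation to the matched means and SDs, giving p = 0.432 and q = 0.431): 0.49, about 2,700 pairs. An age cut holding 35% of patients gives 2 × 0.35 × 0.65 = 45.5%.

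These figures show only that the pairing does not secure balance within a stratum. They do not measure bias.

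**3. Does balance survive within strata?** The simulations used N = 16,989, 64.3% on anastrozole, an assumed age cut of 75, a main-effects PS, 1:1 nearest-neighbour matching with caliper 0.025, and a surgery log-odds ratio averaging 0.95. Matched standardized differences for surgery were:

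| Assumed difference in log-odds ratio, 75+ minus under 75 | Overall | Under 75 | 75+ |
|---|---|---|---|
| 0 | 0.00 | 0.00 | 0.00 |
| 0.4 | 0.00 | −0.06 | +0.11 |
| 0.8 | 0.00 | −0.13 | +0.24 |

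Repeat simulations of the age strata gave −0.06 to −0.08 and +0.11 to +0.12 for a difference of 0.4. For 0.8 they gave −0.12 to −0.16 and +0.22 to +0.24. A generic subgroup holding 40% of patients behaved the same way: 0.00 in both strata with no interaction, and +0.16/−0.11 with a log-odds interaction of 0.6, while the overall value stayed at 0.00.

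**4. From imbalance to hazard ratio.** With a true hazard ratio of 1, surgery prevalences s1 and s0 in the two arms and a dementia hazard ratio h for no surgery, the approximate confounded ratio is [1 + (1 − s1)(h − 1)] / [1 + (1 − s0)(h − 1)]. The documents give no h, so 1.5 and 2.0 are assumptions. Centre the prevalences on the matched 72.2% (SD √(0.722 × 0.278) = 0.448).
- 75+, d = +0.24: the prevalence difference is 0.24 × 0.448 = 0.108, so s1 = 0.776 and s0 = 0.668. With h = 2.0 the ratio is 1.224/1.332 = 0.92; with h = 1.5 it is 0.95.
- 75+, d = +0.11: 0.98 (h = 1.5) and 0.96 (h = 2.0).
- Under 75, d = −0.13: 1.03 and 1.05. With d = −0.06: 1.01 and 1.02.

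The spurious ratio between strata runs from about 0.98/1.01 = 0.97 (mildest setting) to 0.92/1.05 = 0.88 (most extreme of these settings).

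**5. Re-matching within strata.** Fitting the PS and matching separately in each stratum returned surgery differences of 0.00 in both, for a small loss of pairs (for example 5,782 against 5,803).

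**The case against.** The strongest reply is that nothing here shows actual bias. Age and the cardiovascular conditions are listed covariates in Section 6b. A correctly specified PS containing them balances the other covariates within strata in expectation, even when nearly half the pairs are split; the zero-interaction row shows this. A reader might infer from the split pairs that the subgroup estimates are biased or lose information. The documents do not support that: splitting creates no confounding, and no section says that the hazard model is stratified on pair.

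The inputs that produce bias are also assumed. Nothing in the documents shows that the surgery–drug link varies by age or that surgery is related to dementia; Section 6b lists surgery apart from the dementia risk factors. Silence on interactions in Section 7 is not proof of a main-effects model. The cardiovascular stratum was not simulated specifically. The documents give no event counts. With an assumed 200 to 800 events spread evenly over strata and arms, the standard error of the log ratio of hazard ratios is √(16/200) = 0.28 to √(16/800) = 0.14. The worst ratio above (log 0.88 = −0.13) lies within one standard error.

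All of this stands and limits the claim. It does not close the gap: the plan contains nothing that would reveal stratum imbalance if it were present, and the Section 8 table cannot substitute for that check.

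A further reply is that re-matching may meet sparse cells. This is fair. Only 34 anastrozole initiators had targeted therapy, so a 17.7% stratum (the matched ischemic heart disease prevalence) would hold about 6, and immunotherapy is 1 against 1. The fix has to allow for it.

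**Conclusion.** The point holds as a gap in the subgroup analyses. Read together, Sections 3, 7 and 9 imply that the age and cardiovascular-disease hazard ratios reuse one match made for the whole cohort. Section 9 does not say this in terms, but it states no alternative. Balance within each stratum is therefore neither guaranteed nor verified.

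The size depends on assumptions outside the documents. For surgery log-odds ratios differing by 0.4 to 0.8 between age strata, imbalances are roughly 0.06 to 0.16 and 0.11 to 0.24 with opposite signs. At an assumed no-surgery hazard ratio of 2.0, the shift is at most about 8% in a stratum; with no unmodelled interaction there is no systematic bias. For cardiovascular disease the same reasoning applies, but no bias figure is offered.

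Two stronger readings should be resisted. The plan does not fail to produce balance within subgroups; it leaves that balance to an unchecked model. Nor is the primary whole-cohort hazard ratio affected. The change is worth making because it is cheap, but it concerns subsidiary analyses only.

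**What to change.** In Section 9, define the age groups and baseline cardiovascular disease from the Section 6b covariates. For each of these strata:
- re-estimate the PS and re-match 1:1 with the 0.025 caliper inside the stratum;
- collapse or drop covariates too sparse to fit there (immunotherapy and targeted therapy are the obvious candidates);
- fit the subgroup hazard models in the stratum-specific matched sets;
- report the Section 8 standardized differences by stratum.

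The overall matched analysis stays as it is.

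The cost is a few lines of SAP text, plus one re-match and one balance table per stratum, using variables already built. Some pairs will be lost. The simulated loss was under 2%, but the real covariate list is longer, so the actual loss may differ. The subgroup sets will also no longer be exact subsets of the main matched cohort, which the report should state.
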